#### *Measurement and valuation of health-related quality of life*

Health-related quality of life will also be measured with the EQ-5D-5L. This questionnaire measures five self-reported health domains (i.e. mobility, self-care, usual activities, pain/discomfort and anxiety/depression). For the cost-utility analysis (CUA), EQ-5D-5L health states will be converted into utility values using the Dutch tariff. Subsequently, Quality Adjusted Life Years (QALYs) will be estimated by multiplying the duration a patient spent in a certain health state by the utility value of that health state, using linear interpolation between measurement points.

#### Analysis methods

[figure not shown]
Descriptive statistics (e.g. means and proportions) will be used to describe the main characteristics of the clusters (physiotherapists) and trial population (patients). Characteristics of physiotherapists that will be reported are: number of physiotherapists, sex, age, specialization, years of experience working as a physiotherapist, employment status and physiotherapy practice size (where the physiotherapist is employed). The demographic and clinical variables of patients collected in the first questionnaire will be compared between the arms of the trial to investigate potential selection bias. Demographic and clinical baseline measurements of those who are and are not lost to follow-up will be compared to investigate selective attrition.

#### Effectiveness

To determine the overall effectiveness of the Stratified Blended Approach on the combined pain and disability score compared to usual physiotherapy in neck/shoulder patients over 9 months, differences in change scores per arm and time period will be estimated using linear mixed models (LMM) with random effects to control for correlation within patients and physiotherapists. Three levels are identified, consisting of repeated measurements (level 1), nested within patients (level 2), nested within physiotherapists (level 3). Analyses will be adjusted for the values at the first measurement and potential confounders: age, sex, type of complaints (neck or shoulder), pain intensity, duration of symptoms or other variables that are found to be imbalanced at the first measurement between arms.

The statistical analysis of the primary outcome will also be used for the secondary outcomes. However, for dichotomous outcomes, a generalized mixed model (logit link) with the same multilevel structure will be used. Exploratory subgroup analyses will be carried out for hypotheses generating purposes. These analyses will be carried out to investigate potential differences in effectiveness within the three prognostic risk groups (low, medium or high risk), groups based on suitability for blended care (yes or no) and the neck and shoulder patient groups (self-reported predominantly neck or shoulder symptoms), compared to the usual physiotherapy arm.

Table 2. Unadjusted and Adjusted Primary and Secondary Outcome Measures: Improvements and Differences Within and Between arms.

a MVPA = Moderate to Vigorous Physical Activity

b Difference between T0 and follow-up measurements in Stratified Blended Physiotherapy vs. Usual Physiotherapy

c Unadjusted for baseline confounders

d These measures could only be measured after treatment-period, not at T0

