## Trial methods

### Design and randomization

A multicenter, pragmatic, two-arm, parallel-group, cluster randomized controlled trial (cRCT) will be conducted. Physiotherapists will be recruited from primary care physiotherapy practices across all regions of the Netherlands. After recruitment, participating primary care physiotherapy practices will be randomized to either offer the Stratified Blended Approach or usual physiotherapy care by a computer-generated random sequence table generated using SPSS, using 1:1 allocation. The number of physiotherapists per participating practice (dichotomized into '1' and '>1') will be used as a stratification variable. Although individual physiotherapists are identified as clusters, physiotherapy practices will be the unit of randomization in order to prevent contamination between physiotherapists within one practice.

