## Statistical Principles

### Confidence intervals and *P* values

All analyses are described in this statistical analysis plan and are therefore considered *a priori* analyses. If applicable, *post hoc* analyses will be identified as such in the articles.

For all analyses, a two-tailed significance level of  $p < 0.05$  is considered to be statistically significant. All confidence intervals presented will be 95% and two-sided. The assumption of normality will be checked with Q-Q-plots and histograms. The interquartile range will be reported for skewed data.

Statistical analysis will be performed using IBM SPSS 27 or statistical package STATA. During the analyses, the researchers will be blinded to group allocation until the entire analysis will be completed.

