### **Cost-effectiveness**

For the CUA and CEA, missing cost and effect data will be imputed using multivariate imputation by chained equations. The results of the imputed datasets will be pooled using Rubin's rules. LMM, with the same three-level structure as described above, will be performed to estimate cost and effect differences. See the tables below. In order to account for the highly skewed nature of cost data, bias-corrected and accelerated bootstrapping with 5000 replications will be used to estimate 95% confidence intervals around the cost differences. Incremental Cost-Effectiveness Ratios (ICERs) will subsequently be calculated by dividing the differences in costs between trial arms by the difference in QALYs for the CUA and the differences in combined measure of pain and disability for the CEA. The uncertainty surrounding the ICERs will be graphically illustrated by plotting bootstrapped incremental cost-effect pairs on cost-effectiveness planes. Moreover, cost-effectiveness acceptability curves (CEACs) will be constructed to provide a summary measure of the joint uncertainty of costs and effects. CEACs indicate the probability of the Stratified Blended Approach being cost-effective in comparison to usual physiotherapy care at different willingness-to-pay values. To test the robustness of the trial results, several sensitivity analyses will be performed.

**Tabel 3. Mean costs per participant in the Stratified Blended Approach arm and usual physiotherapy (PT) arm and mean differences between both arms during 9 months follow-up**

	SBA (N = ); mean costs in € (SEM)	Usual PT (N = ); mean costs in € (SEM)	Unadjusted mean cost difference in € (95% CI)	Adjusted mean cost difference in € (95% CI)
Intervention a				
Primary healthcare				
Secondary healthcare				
Medication a				
Sport				
Informal care				
Absenteeism				
Presenteeism				
Unpaid productivity				
Healthcare costs b				
Total costs				

aSignificant difference between Stratified Blended Approach and usual PT; bHealthcare costs = intervention costs + primary healthcare costs + secondary healthcare costs + medication costs adjusted for sex, age, BMI, level of education, type of complaints (neck or shoulder), physical functioning at baseline, pain at baseline and utility score at baseline

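### Practices are randomized, but every mixed model stops at the physiotherapist, so the 5% level is not protected if colleagues' outcomes correlate

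*SAP*

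**What the plan says.** On allocation, the SAP (Design and randomization) states: "Although individual physiotherapists are identified as clusters, physiotherapy practices will be the unit of randomization". The reason given is contamination between colleagues. The same section adds: "The number of physiotherapists per participating practice (dichotomized into '1' and '>1') will be used as a stratification variable". Practices with several therapists, all in one arm, are therefore expected.

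On analysis, the SAP (Analysis methods) again names the therapist as the cluster: "main characteristics of the clusters (physiotherapists) and trial population (patients". The primary model (Effectiveness) has random effects for patients and physiotherapists only: "Three levels are identified, consisting of repeated measurements (level 1), nested within patients (level 2), nested within physiotherapists (level 3". Secondary outcomes use the same analysis. For dichotomous outcomes "a generalized mixed model (logit link) with the same multilevel structure will be used". For the economic evaluation (Cost-effectiveness), "LMM, with the same three-level structure as described above, will be performed to estimate cost and effect differences".

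The inferential standard (Confidence intervals and P values) is a two-sided 5% level, and "All confidence intervals presented will be 95% and two-sided".

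**The concern.** Treatment varies only between practices. The variance of the arm difference therefore contains the practice variance divided by the number of practices. A model whose highest level is the therapist treats two colleagues as independent units, although one draw allocated both. If their outcomes correlate through shared patient mix, habits, training or leadership, the comparison is credited with more independent units than were randomized.

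The SAP explains why practices are randomized, but not why practice is then left out of the model. The primary superiority test is at stake, together with the intervals for the secondary outcomes and for the cost and effect differences.

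**Working it through.** **The plan's own figure.** The SAP aims for 238 patients and leaves the calculation to the protocol. That number cannot be reproduced here, and the point does not depend on it.

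**Inputs from the SAP.** Randomization by practice, 1:1; therapists per practice 1 or more than 1; model levels measurement, patient, therapist; alpha 0.05 two-sided.

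**Assumed inputs (not in the SAP).** n = 4 patients per therapist; therapist ICC rT (correlation between patients of one therapist, practice component included) 0.05 to 0.10; practice ICC rP (correlation between patients of different therapists in one practice) 0 to 0.10, never above rT.

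**Formulas.**
- Variance inflation credited by the planned model: 1 + (n−1)·rT.
- Inflation under practice randomization: 1 + (n−1)·rT + e·n·rP, where e = Σm(m−1)/Σm over practices with m therapists. So e = 0 (all single), 2/3 (half with 1, half with 2), 1 (all with 2), 2 (all with 3).
- Ratio R = second ÷ first; actual alpha = 2·[1 − Φ(1.96/√R)].

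**Example.** All practices with 2 therapists, rT = 0.05, rP = 0.05: first = 1 + 3×0.05 = 1.15; second = 1.15 + 1×4×0.05 = 1.35; R = 1.174; √R = 1.083; 1.96/1.083 = 1.81; alpha = 7.0%. With rT = 0.10: R = 1.50/1.30 = 1.154; alpha = 6.8%.

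**Two-sided type I error** (range over rT 0.05–0.10):

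| Therapists per practice | rP 0 | rP 0.01 | rP 0.02 | rP 0.05 | rP 0.10 |
|---|---|---|---|---|---|
| all 1 | 5.0% | 5.0% | 5.0% | 5.0% | 5.0% |
| half 1, half 2 | 5.0% | 5.2–5.3% | 5.5% | 6.2–6.3% | 7.4% |
| all 2 | 5.0% | 5.4% | 5.7–5.8% | 6.8–7.0% | 8.7% |
| all 3 | 5.0% | 5.7–5.8% | 6.4–6.6% | 8.7–9.1% | 12.3% |

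The last column is possible only at rT = 0.10 and is an extreme, because therapists then have no variance of their own.

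**Simulation.** 60 therapists × 4 = 240 patients, therapist random-intercept REML, t reference, one value per patient, no covariates, 40,000 replicates:
- all single: 4.7–5.1%;
- half 1, half 2: 6.1–6.2% at rP 0.05;
- all 2: 5.3–5.4% at rP 0.01, 6.7–6.9% at 0.05, 8.8% at 0.10;
- all 3: 8.8–9.0% at rP 0.05, 12.7% at 0.10.

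**Second set of assumptions.** 5 patients per therapist, 2 therapists per practice, practice ICC 0.05, additional therapist ICC 0.03. Credited inflation is 1 + 4×0.08 = 1.32; correct inflation is 1.32 + 1×5×0.05 = 1.57. The standard error is √(1.32/1.57) = 0.917 of its correct value, and alpha is 7.2%. Effective sample size is 238/1.57 = 152, not 238/1.32 = 180. Over 3–5 patients per therapist, 2–4 therapists per practice and practice ICC 0.01–0.05, alpha runs from 5.3% to 12.4%. In simulated null trials from this range, a t test on practice means kept 4.8–5.2%.

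**The case against.** The strongest reply is that the choice is open, not hidden: the SAP says itself that therapists are taken as clusters although practices are randomized. The unseen protocol may also hold an ICC or a reason to regard practice variance as negligible. That is fair, and the absence of those figures is not held against the SAP. It does not cure the model, which the SAP specifies itself and which does not match its own randomization.

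Other points stand in part:
- All magnitudes are assumed. With a mix of one- and two-therapist practices and a practice ICC of 0.01–0.02, the error is only 5.2–5.5%. The stratification factor shows that single-therapist practices are expected, so the mixed scenario deserves more weight than the all-2 and all-3 rows.
- The percentages are two-sided. False superiority of the new approach is half of each: 7.0% means 3.5% against 2.5%.
- The simulation has one value per patient and no covariates, whereas the SAP adjusts for the first measurement and patient characteristics. Adjustment may absorb some practice variance, but nothing guarantees it.
- Cost intervals come from a bootstrap whose resampling unit is not stated. They are too narrow if patients or therapists are resampled and practice variance is present; the calculation above does not model that bootstrap.

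**Conclusion.** The concern holds. The analysis does not respect the unit of randomization in the primary, secondary, logit or economic models, and nothing else in the SAP makes up for it. The mismatch is certain from the text; its size is not. Exact protection of the 5% level requires zero practice variance or one therapist in every practice. Near-nominal error is also kept when both the practice ICC and the share of multi-therapist practices are small. At a practice ICC of 0.05, error is about 6–7% with one or two therapists per practice and about 9% with three, on the assumptions above. Because the validity of the primary test is at issue, this should be settled before the analysis; under the SAP's own rule, a practice level added afterwards would be post hoc.

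**What to change.** - Add a random intercept for practice to all mixed models, or use practice-clustered inference, with a small-sample degrees-of-freedom correction such as Satterthwaite or Kenward-Roger where available.
- Therapist and practice effects cannot be separated in single-therapist practices. State in advance that if a level must be dropped for convergence, practice is kept.
- State that the cost bootstrap resamples whole practices.
- For outcomes with one value per patient (QALYs, 9-month total costs, 3-month-only outcomes), give the levels as patients, physiotherapists, practices.

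No new data are needed, since each therapist's practice is known from randomization. The work is SAP wording plus one further random term, which must also be carried through the logit, imputed and bootstrapped models.

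The price is precision. Intervals widen by √R, and a comparison with 80% power when practice is ignored has power Φ((1.96 + 0.84)/√R − 1.96). With two therapists in every practice:
- practice ICC 0.01: about 2% wider, power about 79%;
- 0.05: 7–8% wider, 73–74%;
- 0.10: 14% wider, 69%.

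With three therapists and ICC 0.10, intervals are 27% wider and power is about 60%. If practice variance is negligible, the loss is close to nil.

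### The linear mixed models include neither the randomized unit (practice) nor the only stated stratifier (practice size): mainly an error-control gap, with a minor, conditional calibration point

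*SAP*

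**What the plan says.** **Randomization.** Under Design and randomization, practices are allocated 1:1, and the number of physiotherapists per practice, split at 1 versus more than 1, "will be used as a stratification variable". No other stratifier is stated. The section calls individual physiotherapists the clusters but adds that "physiotherapy practices will be the unit of randomization in order to prevent contamination between physiotherapists within one practice".

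**Model.** Under Effectiveness, the levels are repeated measurements, within patients, "nested within physiotherapists (level 3"). There is no practice level. The Cost-effectiveness section takes over the structure: "LMM, with the same three-level structure as described above".

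**Covariates.** The effectiveness list reads "Analyses will be adjusted for the values at the first measurement and potential confounders: age, sex, type of complaints (neck or shoulder), pain intensity", then duration of symptoms, "or other variables that are found to be imbalanced at the first measurement between arms". Practice size is not named. It is also absent from the adjustment list in the Table 3 footnote.

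**Other use of practice size.** Under Analysis methods, "physiotherapy practice size (where the physiotherapist is employed") is one of the physiotherapist characteristics to be described. The arm comparison there concerns patients: "The demographic and clinical variables of patients collected in the first questionnaire will be compared between the arms of the trial".

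**The concern.** Arm is assigned to whole practices. Anything shared by the physiotherapists of one practice (case mix, local habits, organization) therefore falls entirely within one arm. A model that treats those physiotherapists as independent counts more independent units than were randomized. If such shared variation exists, the SE of the arm effect is too small and type I error exceeds 5%. The plan expects the situation to arise: it has a stratum for practices with more than one physiotherapist and chose the practice as unit because of contact between colleagues.

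The stratifier acts in the other direction. If practice size predicts outcome, stratified allocation removes that source of variation from the arm comparison, but a model without the variable leaves it in the error term and reports an SE slightly too large. The imbalance clause does not secure its entry: the clause is data-driven, the planned comparison covers patient questionnaire variables, and stratification makes imbalance in this variable unlikely.

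Because the two omissions push the SE in opposite directions, adding only the covariate can make error control worse.

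**Working it through.** **Inputs from the SAP:** 238 patients (Sample size); two-sided 5% level; 1:1 allocation. **Not in the SAP, so assumed and varied:** ICCs, patients per physiotherapist, physiotherapists per practice, share of patients in one-physiotherapist practices, and effect of practice size. The SAP leaves its sample size calculation to the protocol, so 238 cannot be reproduced here. Nothing is held against it for that.

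**Step 1. Missing practice level.** Set the outcome variance to 1. Let *n* be patients per physiotherapist, *m* physiotherapists per practice, *t* = 0.02 the physiotherapist ICC, *p* the practice ICC, and *e* = 1 − *t* − *p*.

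- Correct variance of the arm difference: (4/238) × (*e* + *nt* + *nmp*)
- Variance reported by the physiotherapist-only model: about (4/238) × (*e* + *n*(*t* + *p*))
- Type I error: 2 × [1 − Φ(1.96 × reported SE / correct SE)]

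Worked case, *n* = 5, *m* = 2, *p* = 0.03. Correct: (4/238) × (0.95 + 0.10 + 0.30) = (4/238) × 1.35, SE 0.1506. Reported: (4/238) × (0.95 + 0.25) = (4/238) × 1.20, SE 0.1420. The correct SE is 6.1% larger and type I error is 6.5%.

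| n | m | p | Correct SE | Reported SE | Correct larger by | Type I error |
|---|---|---|---|---|---|---|
| 3 | 1.5 | 0.01 | 0.1344 | 0.1335 | 0.7% | 5.2% |
| 5 | 2 | 0.03 | 0.1506 | 0.1420 | 6.1% | 6.5% |
| 8 | 3 | 0.05 | 0.1962 | 0.1582 | 24.0% | 11.4% |
| 5 | 1 | 0.03 | 0.1420 | 0.1420 | 0% | 5.0% |
| 5 | 2 | 0 | 0.1347 | 0.1347 | 0% | 5.0% |

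The first and third rows are the ends of the range examined. The last two show when nothing is wrong.

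**Step 2. Missing stratifier.** Let *d* be the difference between strata in SD after the planned adjustment, *q* the share of patients in one-physiotherapist practices, and *r* = 0.05 the total residual ICC, with 5 patients per physiotherapist and strata balanced by arm.

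*f* = *d*²*q*(1−*q*) / [*d*²*q*(1−*q*) + *r* + (1−*r*)/5]; SE overstatement = 1/√(1−*f*) − 1.

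- *d* = 0.2, *q* = 0.50: *f* = 0.010/(0.010 + 0.24) = 4.0%; SE 2.06% too large.
- *d* = 0.2, *q* = 0.15: *f* = 0.0051/0.2451 = 2.1%; SE 1.06% too large.
- *d* = 0.1, *q* from 0.15 to 0.50: SE 0.27% to 0.52% too large.
- *d* = 0: no effect.

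**Step 3. Both omissions together.** Simulation of 48 physiotherapists with 5 patients each in four layouts: 8, 24, 6 or 24 one-physiotherapist practices, plus respectively 20 × 2, 12 × 2, 14 × 3 or 8 × 3. That gives 28, 36, 20 and 32 practices. Total ICC was 0.05, of which 0.01-0.03 is practice variance; *d* = 0.2; REML; degrees of freedom are physiotherapists or practices minus fixed effects.

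| Model | Type I error |
|---|---|
| As planned | 4.9-7.3% |
| Planned + practice size only | 5.3-7.6% |
| Planned + practice random effect only | 3.6-4.3% |
| Both | 3.7-4.9% |

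A second simulation (12 one- and 18 two-physiotherapist practices, *t* = 0.02, z-test) agrees in direction. At *p* = 0.05 and *d* = 0.3, type I error was 6.9% as planned, 7.7% with the covariate alone and 5.8% with both. Across its scenarios, adding both terms changed the mean reported SE by −0.4% to +7.2%. The estimate's true spread hardly moved (for example 0.1582 versus 0.1580).

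**Step 4. Degrees of freedom.** With 48 physiotherapists and two fixed effects (intercept and arm) there are 46 df and t = 2.013. With 36 or 20 practices and three fixed effects there are 33 or 17 df, and t = 2.035 or 2.110. The quantile is 1.1% or 4.8% larger.

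**The case against.** **The choice looks deliberate, and practice variance may be negligible.** The SAP names physiotherapists as the clusters. If practices share little beyond what their physiotherapists bring, or mostly contribute one physiotherapist, the planned model is adequate. This stands as a limit on size: the SAP settles neither question. It does not remove the gap, since the reason given for randomizing practices concerns contamination and is no argument for independence of colleagues' patients.

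**The change costs power.** In the four layouts above, both terms together widened the average 95% interval by 2.1-16.1% against the planned model and lowered power at a 0.43 SD effect by 1.3-9.0 points. Even with zero practice variance, the second simulation gave a mean SE of 0.1399 against 0.1362 (2.7% larger) and type I error of 4.3% against 4.9%. This stands. Where the planned test is inflated, part of the lost power was never legitimate; where it is not, the loss is the price of protection.

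**A reader might infer that the two terms together raise precision, or save patients.** They do not. The practice random effect is a validity correction that usually widens the interval. The covariate only removes an overstatement of the SE; with balanced strata the estimate's true spread is practically the same with or without it.

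**A reader might also infer that omitting the stratifier biases the result.** In the linear models with strata balanced by arm it does not. The SAP nowhere says that practice size is prognostic.

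**A fourth level complicates other models.** In a logit model, an added term changes the conditional odds ratio. In the economic models it must coexist with multiple imputation and 5000 bootstrap replications. This stands, and it is why the point is confined to the linear models.

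**Conclusion.** The point holds as a gap between how the trial is randomized and how the linear models are specified.

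- **Main issue, error control:** type I error of roughly 5-11% under assumed practice ICCs of 0.01-0.05, 1.5-3 physiotherapists per practice, 3-8 patients per physiotherapist and a physiotherapist ICC of 0.02. No inflation if practice variance is zero or every practice has one physiotherapist.
- **Secondary issue, SE calibration:** a reported SE about 1-2% too large if practice size shifts the outcome by 0.2 SD after the planned adjustment, 0.3-0.5% at 0.1 SD, nil at 0. This adds no information, and correcting it alone can slightly worsen type I error.

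It would go too far to say that the primary test is inflated as planned. The documents give no ICC and no number of physiotherapists per practice, so the SAP only leaves that risk uncontrolled. The sizes are illustrations over stated ranges, and none is claimed for the logit or economic models. The change is worth considering before the database is locked.

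**What to change.** In the linear primary and secondary models, make these changes together:

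1. Add a random effect for practice, with physiotherapists nested within practices.
2. Add practice size (1 versus more than 1, as coded at randomization) as a prespecified fixed effect, whatever the observed balance.
3. Base the test and interval for the arm effect on practice-level degrees of freedom, and say in advance what is done if the practice variance is estimated as zero.

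Do not add the covariate without the practice level. Align the linear cost and effect models where the added level can be fitted alongside imputation and bootstrapping.

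**Cost:** a few lines in the SAP, plus one variance component and one fixed effect per model. No new data are needed, since practice membership and size were required to randomize. The real price is a confidence interval that will usually be wider than under the planned model (1.1-4.8% from the t quantile alone with 20-36 practices), with correspondingly lower nominal power.

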### Sample size

We aim to reach a sample size of 238 patients. The full sample size calculation is provided in the trial protocol.

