#### *Demographic and clinical characteristics*

- Patient characteristics are only collected in the first questionnaire and include various demographic and clinical variables, including: age, sex, education level, duration of complaints, weight, height and co-morbidities.
- The risk of persistent disabling pain will be assessed with the Keele STarT MSK Tool (i.e. low, medium or high risk). The Keele STarT MSK Tool is part of the Stratified Blended Approach and is additionally included in the data collection.
- As part of the data collection, patients' suitability for e-Exercise (blended care) will be measured by two self-developed questions as substitute for the Dutch Blended Physiotherapy Checklist. It is not possible to use the Dutch Blended Physiotherapy Checklist as a measurement instrument, because it is a tool to guide physiotherapists in their clinical reasoning while setting up a personalized blended physiotherapy treatment,

thus not a patient reported outcome measure. Therefore, this cannot be measured in the control arm and substitute questions will be used. The following questions will be assessed in the first questionnaire to measure smartphone or tablet access and usage: 'Do you own a smartphone or tablet? (yes/no)' and 'How many apps do you use regularly (weekly) on your smartphone or tablet? (none/1-3 per week/4-10 per week/more than 10 per week)'.

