#### *Other outcomes*

- Compliance to the smartphone app with e-Exercise modules in the Stratified Blended Approach arm will be assessed by quantitative data on the usage. These data will automatically be stored on the backend of the app. Additionally, all patients will be asked in the first follow-up questionnaire whether they received and used an app or paper-based workbook as part of their physiotherapy treatment.
- The content and intensity of physiotherapy care will be described from trial case report forms, for both trial arms, filled out by the physiotherapists at the end of the treatment period or after 3 months. Information of the risk of persistent disabling pain, the suitability for blended care, the physiotherapists diagnosis of the presenting problem, the number of physiotherapy sessions, deviations from the study protocol, and content of the physiotherapy sessions will be collected. Number of physiotherapy sessions and content of the physiotherapy sessions will be presented in a table, separately for the 3 risk groups and per trial arm.

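### The exploratory subgroup plan names no arm-by-subgroup interaction, and blended-care suitability (yes or no) has neither a chosen source nor a cut-off

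*SAP*

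**What the plan says.** The Effectiveness section under Analysis methods introduces the subgroup work as exploratory: "Exploratory subgroup analyses will be carried out for hypotheses generating purposes". It then states the aim: "These analyses will be carried out to investigate potential differences in effectiveness within the three prognostic risk groups (low, medium or high risk"). The same sentence adds two suitability groups (yes or no) and two self-reported region groups (neck or shoulder), all compared with usual physiotherapy. No interaction term or test of heterogeneity is named anywhere in the SAP.

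The section Confidence intervals and P values applies one threshold throughout: "For all analyses, a two-tailed significance level of" 0.05. It makes no exception for subgroups. It also treats every analysis described in the SAP as a priori and says any other will be labelled post hoc.

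Two sections deal with suitability:

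- Demographic and clinical characteristics explains that the blended physiotherapy checklist guides therapists' reasoning and is not a patient-reported measure, so "this cannot be measured in the control arm and substitute questions will be used". The substitutes are two items in the first questionnaire: device ownership (yes/no) and weekly app use (four categories).
- Other outcomes describes a case report form that physiotherapists complete in both arms when treatment ends or at three months. Among its items: "Information of the risk of persistent disabling pain, the suitability for blended care".

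**The concern.** The stated question is whether the effect differs between kinds of patient. The only comparison described is intervention against usual care inside each kind. Those results do not answer the question, because two subgroups with the same true effect can easily fall on opposite sides of 0.05. Since unlisted analyses become post hoc, an interaction test added later would carry that label, while the within-subgroup comparisons would count as planned.

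The suitability factor has a second problem. The analyst would have to choose between the patient items and the therapist's form, and then decide how to turn the answers into yes or no. The form is completed by the treating therapist after randomization and after treatment, so its suitability entry could be influenced by how treatment went. The SAP gives no rule for either choice.

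These subgroups will be read closely. The Background and rationale rests the intervention on matching content to risk and delivery mode to suitability, and those are two of the three subgroup factors.

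**Working it through.** **Inputs from the SAP.** Sample size: "We aim to reach a sample size of 238 patients". Two-sided alpha 0.05. Practices randomized "using 1:1 allocation". Subgroup levels: 3 (risk) + 2 (suitability) + 2 (region) = 7.

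**The plan's own figure.** The 238 cannot be reproduced here, because "The full sample size calculation is provided in the trial protocol" and the SAP gives no effect size, SD, power, intracluster correlation or dropout. The SAP states no subgroup sizes or subgroup power.

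**Assumptions.** Overall power of 80%, with 90% as a check; subgroup shares as shown; the same true effect in every subgroup; clustering ignored.

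**Step 1: power within a subgroup.** At 80% overall power the expected z is 1.960 + 0.842 = 2.802. For a subgroup with share f of the patients, power = Φ(2.802√f − 1.96) + Φ(−2.802√f − 1.96).

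- f = 1/2: 2.802 × 0.707 = 1.981, power 0.508.
- f = 1/3: 2.802 × 0.577 = 1.618, power 0.366.

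**Step 2: chance of conflicting verdicts.** This is the probability that at least one level is significant and at least one is not: 1 − Πp − Π(1 − p).

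- Two equal groups: 1 − 0.508² − 0.492² = 0.50.
- Three equal groups: 1 − 0.366³ − 0.634³ = 0.70.

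| Split | 80% overall power | 90% overall power |
|---|---|---|
| 50/50 | 0.50 | 0.47 |
| 70/30 | 0.55 | 0.54 |
| three equal | 0.70 | 0.75 |
| 40/40/20 | 0.71 | 0.76 |

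An interaction test would falsely report a difference in 5% of trials for each factor.

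**Step 3: all three factors together.** A simulation used 10,000 trials of 238 patients, with risk 40/40/20, suitability 70/30, region 50/50 and the factors independent of each other. With a uniform effect at 80% overall power, at least one factor gave conflicting verdicts in about 86% of trials. At least one of the three interaction tests was falsely significant in 14.7%, close to 1 − 0.95³ = 14.3%.

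**Step 4: false positives when there is no effect at all.** Seven independent tests give 1 − 0.95⁷ = 30.2%. The three factors divide the same patients, however, and the simulation gives 24.6%, which is the fairer figure. This rate concerns any treatment effect in any subgroup, a different null hypothesis from heterogeneity, so it should not be set directly against the 14.3%.

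**Step 5: what an interaction test could detect.** For a two-level interaction as large as the overall effect, z = 2.802 / √(1/f₁ + 1/f₂).

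- 50/50: 2.802 / 2 = 1.401, power 0.29.
- 70/30: 2.802 / 2.182 = 1.284, power 0.25.

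At 90% overall power these become 0.37 and 0.32.

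**Step 6: the suitability sources side by side.**

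| | First-questionnaire items | Case report form |
|---|---|---|
| Completed by | patient | treating physiotherapist |
| When | first questionnaire, requested within a week of starting treatment | end of treatment or after 3 months |
| Arms | both | both |
| Rule giving yes/no | none stated | none stated |
| Named as the subgroup source | no | no |

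**The case against.** The strongest defence is that the SAP is silent on an interaction rather than opposed to one. It does not say that separate models will be fitted or that p-values will be compared between subgroups, and an aim of finding differences in effectiveness could be met with an interaction term. A reader might infer that the SAP adopts verdict-comparing as its method. The text does not go that far, and the fault is under-specification. The silence still matters because of the SAP's own rule on what counts as a priori.

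A reader might also infer that suitability comes from different sources in the two arms, so that the groups are not comparable. The documents do not support this. What cannot be measured in controls is the checklist, and both the substitute items and the form cover both arms. Comparability would fail only if one source were used in one arm and another in the other, which no section proposes. The questionnaire items are the more natural reading, since the SAP presents them as its measure of suitability, while the form appears among items to be described. Nor does the problem reach the other factors: the risk tool is part of the trial's data collection and region is self-reported.

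Finally, the analyses are labelled exploratory, and interaction tests in a trial of this size would seldom detect real heterogeneity. Both points stand. They limit the consequence, but they do not make within-subgroup p-values informative about differences.

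**Conclusion.** The point holds as under-specification of an exploratory analysis. The SAP asks whether effects differ between subgroups and names no analysis that tests it. Under a uniform true effect, significance verdicts would conflict in about 50% of trials for two equal groups and 70% for three. These figures rest on an assumed 80% overall power, assumed subgroup shares and no clustering. At 90% power they are 47% and 75%, so the conclusion does not depend on which power is assumed. They describe what happens if within-subgroup p-values are read as evidence of a difference. They do not show that the subgroup results will mostly be noise.

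Separately, the suitability subgroup has two possible sources, no choice between them and no cut-off. The primary analysis is unaffected by either fault.

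**What to change.** In the Effectiveness section, state that for each factor one mixed model will be fitted to all patients with arm by subgroup (by time) terms, keeping the planned multilevel structure. Report the interaction result and the effect in each subgroup with its 95% interval, all labelled exploratory, and make no claim from within-subgroup p-values. Add that interaction power is low (about 25–29% for a two-level interaction as large as the overall effect, at an assumed 80% overall power), so a non-significant interaction does not show that effects are equal.

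Define suitability in both arms from the two first-questionnaire items, with an explicit yes/no cut-off fixed before unblinding. Because the SAP keeps analysts blinded until the whole analysis is complete, it is better still to fix the cut-off before any outcome is analysed. Keep the case report form's suitability item and the app or workbook assignment descriptive.

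This changes SAP wording only. It needs no new data and uses three models per outcome in place of seven within-subgroup comparisons.
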